7.2.4 Efficacy Analysis

The efficacy endpoints to be analyzed are:

- Proportion of subjects exhibiting complete clearance of all treated molluscum lesions (baseline and new) on or before Week 12 (EOS).
- Proportion of subjects exhibiting a 90% or greater reduction of all treated molluscum lesions (baseline and new) at the EOS visit.
- Percent reduction of treated molluscum lesions from baseline at the EOS visit.
- Change from baseline in the number of treated molluscum lesions at the EOS visit.

- Change from baseline in quality of life and impact of skin disease as measured by the CDLQI assessment.
- Spread to siblings as measured by any new occurrence of molluscum in siblings of subject.

Data will be summarized using descriptive statistics and 95% confidence intervals for the above endpoints using the Intent-to-Treat Population.

7.2.5 Safety Analysis

Adverse event data for the safety population will be listed individually, and the incidence of adverse events will be summarized by treatment, using frequency counts. When calculating the incidence of adverse events, each adverse event will be counted only once for a given subject. If the same adverse event occurs on multiple occasions for a subject, the occurrence with the highest severity and relationship to Study drug will be reported. If two or more adverse events are reported as a unit, the individual terms will be reported as separate events. The Medical Dictionary of Regulatory Activities (MedDRA) (Version 19.1 or higher) will be used for coding AEs. Changes in vital signs, from baseline to the end of the study will be examined. Treatment-emergent changes from normal values to abnormal values will be identified as described in [Section 2.3.1](#).

7.2.6 Interim Analysis

No interim analysis is planned for this study.

7.2.7 Handling of Missing Data

The procedures for handling missing data will be described in the Statistical Analysis Plan.

7.3 INFORMED CONSENT AND AUTHORIZATION FOR USE AND DISCLOSURE OF PROTECTED HEALTH INFORMATION

Written assent and informed consent and authorization of use and disclosure of protected health information must be obtained from each subject (or the subject's legally acceptable representative) before performing any study-specific screening/baseline period evaluations. One copy of the signed informed consent form (and IRB-required assent form) and authorization for use and disclosure of protected health information form will be given to the subject, and the investigator will retain the original. The informed consent form and authorization for use and disclosure of protected health information, which is prepared by the investigator or the site, must have been reviewed and approved by the sponsor, the study monitor, and the investigator's IRB and privacy board (if separate from the IRB) before the initiation of the study. The informed consent form must contain the 20 elements of informed consent described in International Council for Harmonisation E6, Section 4.8. The authorization for use and disclosure of protected health information must contain the elements required by Title 45 of the Code of Federal Regulations, Section 164.508(b), and any local regulations for valid authorizations.

7.4 STUDY DOCUMENTATION**7.4.1 Investigator Information**

Investigator information is included in the Investigator Brochure and Manual of Operations, which is updated as needed.

7.4.2 Investigator's Study Files

Documentation about the investigator and study staff, the IRB, and the institution is required before site initiation. Copies of these documents will be kept on-site in site-specific binders or electronic folders, along with the following supplemental information: a list of investigator's obligations, the Investigator's Brochure, the clinical protocol and amendments, safety information, information about investigational product, biological samples, and the research laboratory, the study procedures manual and study logs, CRFs, records of monitoring activities, and correspondence between sponsor or study monitor and the investigator. The investigator is responsible for maintaining audit trails of all electronic data systems used for source documentation.

7.4.3 Case Report Forms and Source Documentation

The investigator must make study data accessible to the site monitor, other authorized representatives of the Sponsor, and the appropriate regulatory authority inspectors. The CRF for each subject will be checked against source documents at the site by the site monitor, and a final copy of the CRF will be signed by the investigator.

7.4.4 Retention of Study Documents

According to International Council for Harmonisation E6 guidance, all eCRFs, as well as supporting paper and electronic source documentation and administrative records, must be retained by the investigator until at least 2 years following notification that either the appropriate regulatory authority has approved the product for the indication under study, the sponsor has discontinued clinical development of the product, or notification that the marketing application was not approved.

These documents should be retained for a longer period, however, if required by the applicable regulatory requirements or by an agreement with the sponsor. The Sponsor is responsible for informing the investigator and institution as to when these documents no longer need to be retained. No study documents will be destroyed or moved to a new location without prior written approval from the Sponsor. If the investigator relocates, retires, or withdraws from the study for any reason, all records required to be maintained for the study should be transferred to an agreed-upon designee, such as another investigator at the institution where the study was conducted.

7.5 CONFIDENTIALITY

7.5.1 Data

The investigator must keep all information confidential about the nature of the proposed investigation provided by the Sponsor or study monitor to the investigator (with the exception of information required by law or regulations to be disclosed to the IRB, the subject, or the appropriate regulatory authority).

7.5.2 Subject Anonymity

The anonymity of participating subjects must be maintained. Subjects will be identified by an assigned subject number on CRFs and other documents retrieved from the site or sent to the study monitor, Sponsor, regulatory agencies, central laboratories, or blinded reviewers. Documents that identify the subject (e.g., the signed informed consent form) must be maintained in strict confidence by the investigator, except to the extent necessary to allow auditing by the appropriate regulatory authority, the study monitor, or sponsor representatives.

7.6 PROTOCOL COMPLIANCE

Substantive changes in the protocol include changes that affect the safety of subjects or changes that alter the scope of the investigation, the scientific quality of the study, the experimental design, dosages, assessment variable(s), the number of subjects treated, or the subject-selection criteria. Such changes must be prepared as a protocol amendment by the Sponsor and implemented only upon joint approval of the sponsor and the investigator. A protocol amendment must receive IRB approval before implementation. In parallel with the IRB approval process, the protocol amendment will be submitted to the appropriate regulatory authority as an amendment to the regulatory submission under which the study is being conducted. If a protocol amendment requires changes in the informed consent form, the revised informed consent form prepared by the investigator must also be approved by the sponsor, study monitor, and the IRB before implementation.

Departures from the protocol are allowed only in situations that eliminate an immediate risk to a subject and that are deemed crucial for the safety and well-being of that subject. The investigator or the attending physician also will contact the medical monitor as soon as possible in the case of such a departure. These departures do not require preapproval by the IRB; however, the IRB and medical monitor must be notified in writing as soon as possible after the departure has been made. In addition, the investigator will document in the subject's CRF the reasons for the protocol deviation and the ensuing events.

7.7 STUDY MONITOR FUNCTIONS AND RESPONSIBILITY

The study monitor, in accordance with the sponsor's requirements, will ensure that the study is conducted and documented properly by carrying out the activities outlined in International Council for Harmonisation E6 guidance.

7.8 GENERAL INFORMATION

The investigator should refer to the Investigator's Brochure, study procedures manual, and any other information provided about this investigational product and details of the procedures to be followed during this study.

10.5.	Subject Reported Spread of Molluscum Lesions.....	16
11.	Safety Analysis	17
11.1.	Extent of Exposure	17
11.2.	Adverse Events	17
11.3.	Targeted Adverse Events- Local Skin Reactions.....	18
11.4.	Patient Evaluation of Response to Treatment (PERIT)	19
11.5.	Vital Signs	19
11.6.	Physical Examination	19
11.7.	Prior and Concomitant Medications	19

List of Abbreviations

AE	Adverse Event
ANCOVA	Analysis of Covariance
ATC Class	Anatomical/Therapeutic/Chemical Class
BMI	Body Mass Index
CDLQI	Children's Dermatology Life Quality Index
CSR	Clinical Study Report
EDC	Electronic Data Capture
EOS	End of Study
ERT	Evaluation of Response to Treatment
GC/MS	Gas Chromatography/Mass Spectrometry
IRB	Institutional Review Board
ITT	Intent to Treat
LLOQ	Lower Limit of Quantification
LOCF	Last Observation Carried Forward
LSR	Local Skin Reactions
MedDRA	Medical Dictionary for Regulatory Activities
mm	Millimeter
MMRM model	Mixed Model, Repeat Measures model
PERIT	Patient Evaluation of Response to Investigational Treatment
RTF	Rich Text Format
SERT	Safety Evaluation of Response Treatment
TEAE	Treatment Emergent Adverse Event
TFL	Tables, Figures, Listings

Verrica Pharmaceuticals, Inc.
Protocol: VP-102-103

Statistical Analysis Plan

04APR2018

WHO

World Health Organization

1. Introduction

Verrica Pharmaceuticals, Inc. is conducting a study under the protocol name “A Phase 2, Open-Label Study to Evaluate the Safety, Efficacy and Systemic Exposure of VP-102 Topical Film Forming Solution [0.7% (w/v) cantharidin] in Subjects (2 years and older) with Molluscum Contagiosum”. The study background, design and subject assessments for the study are described in the study specific protocol.

The statistical methods to be implemented during the analyses of data collected within the scope of this study (VP-102-103) will be outlined in this document. The purpose of this plan is to provide specific guidelines from which the statistical analysis will proceed. Any deviations from this plan will be documented in the clinical study report.

2. Study Rationale and Objectives

2.1. Study Rationale

The protocol states: “For many dermatologists, 0.7% w/v cantharidin has been the treatment of choice for molluscum for decades. However, cantharidin remains an unapproved drug, and there is no reliable or controlled source on the market. This study will evaluate VP-102, a controlled, highly-pure, standardized form of topical cantharidin manufactured under good manufacturing practices in order to address the problems associated with currently available compounded cantharidin products and the needs of patients and medical professionals.”

2.2. Study Objectives

2.2.1. Primary Objectives

The primary objective of this study is to determine the presence or absence of systemic cantharidin exposure from a single 24-hour dermal application of VP-102 topical film-forming solution [0.7% (w/v) cantharidin] (VP-102) when applied to molluscum contagiosum (molluscum) lesions on pediatric subjects 2 years old and older.

2.2.2. Secondary Objectives

The secondary objectives of this study are:

- to assess the safety of VP-102, when applied once every 21 days for up to 4 applications, to treated molluscum lesions on subjects 2 years old and older by assessing adverse events including expected local skin reactions, physical examinations and concomitant medications throughout the study compared to baseline.
- To assess the efficacy of VP-102 in the treatment of molluscum lesions as assessed by clearance or reduction of treated molluscum lesions as compared to baseline.

- To assess the impact of VP-102 treatment on quality of life of subjects as assessed via the administration of the Children's Dermatology Life Quality Index (CDLQI).

3. Study Design

This is a Phase 2 study that will be conducted in the United States to determine the systemic exposure, efficacy, safety and impact on quality of life of VP-102 (0.7% cantharidin) following treatment of molluscum lesions for up to 4 treatments, 21 days apart, with VP-102 in up to 40 subjects (2 years or older). Subjects to be included in the Exposure group must have at least 21 lesions treated at Day 1 to qualify. The Standard treatment group will consist of subjects with fewer than 21 lesions treated at Day 1. Duration of molluscum lesions prior to Day 1 will be recorded but will not be an inclusion/exclusion requirement.

Study drug, VP-102, will be supplied in single-use applicators, with one applicator sufficient to treat at least 50 molluscum lesions. If required due to the number and size of lesions, a second single-use applicator may be used. No more than 2 applicators will be permitted per subject per treatment. In the Exposure group, blood samples for systemic exposure evaluation will be collected on Day 1, prior to the Study drug application (T=0), and 2 (\pm 30 minutes), 6 (\pm 1 hour) and 24 (\pm 3 hours) hours post-application. The film-forming Study drug solution will be applied and left on the lesions for approximately 24 hours before the subject and/or parent/guardian washes the dried film off the lesions with soap and warm water. For those subjects in the Exposure group, the dried film will be removed after the 24-hour blood draw is obtained. Study drug treatment may be removed prior to the 24-hour time point in the event significant blistering, uncontrollable pain or treatment emergent AEs are experienced.

Molluscum lesions will be treated without occlusion in all anatomic areas including the face, trunk, back, arms, legs, hands, feet, genital region and buttocks as long as the physician feels it is safe to do so.

The study duration from Day 1 through the EOS visit is up to 12 weeks. Pre-study screening for eligibility (informed consent, inclusion/exclusion criteria and medical history) will occur up to 14 days before, or on Day 1/Study drug administration. Subjects will be treated with application to molluscum lesions every 21 days (\pm 4 days) for a maximum of 4 treatment sessions. Subjects that completely clear prior to ~Day 84 will

complete their EOS visit on that day. In the event of scheduling conflicts in subsequent visits after the Day 1 treatment, subjects may be scheduled on 21 ± 4 days following their previous treatment. The next study visit should then be scheduled 21 days after the previous treatment.

Assessment of local skin reactions (LSR) will be performed by the investigator or trained member of the research team at each treatment visit and the EOS visit. LSRs will be recorded as adverse events. LSRs will include the following adverse events: blistering, pain, pruritus, erythema, edema, erosion/ulcerations, flaking/scaling/dryness, scabbing/crusting and pigmentation changes. A Skin Quality Assessment will also be performed as part of the review of LSRs and will assess erythema, flaking/scaling/dryness, scabbing/crusting, hyperpigmentation, hypopigmentation and scarring, if applicable.

Parent/subject quality of life and measure of impact of skin disease will be assessed with the CDLQI prior to application of Study drug at each treatment session and at the EOS visit. Subjects will also complete a Safety Monitoring Questionnaire at Visits 2-5.

Subjects will be given a 24-hour phone number to call the investigator or a clinical research team member in the event of questions or AEs. Evaluations will also be provided by the subject or parent/guardian using the Patient Evaluation of Response to Investigational Treatment (PERIT) form the following day after Study drug application. Parents will also be asked to take and send photos via text or e-mail to the study team for assessment during the 24-hour follow-up call. All observed AEs, local skin reactions and parent-reported AEs will be recorded.

Parents or guardians must provide informed consent, and pediatric subjects older than 5 years must provide assent as required by the IRB before any study procedures are conducted. Subjects must meet all study eligibility criteria through a complete review of pertinent medical history, a symptom/sign evaluation, and limited physical examination.

4. Determination of Sample Size

The primary objective of the study is to determine the presence or absence of systemic cantharidin exposure from application of VP-102. Thus, power calculations were not performed. There will be up to 40 subjects enrolled with the goal of 16 completing all blood draws in the Exposure group. Any subject in the Exposure group who does not

complete all blood draws may continue to receive treatment, but will be replaced. At least 3 subjects in the Exposure group will be from 2-5 years of age.

5. Statistical Methods

The statistical analyses will be reported using summary tables, figures and listings (TFLs). Numbering for TFLs will be based on the recommended numbering convention provided by the International Conference on Harmonization. Continuous variables will be summarized with means, standard deviations, medians, minimums and maximums.

Categorical variables will be summarized by counts and percent of subjects in corresponding categories. Where appropriate, 95% confidence intervals will be included. Missing values are not considered for percent calculations, unless stated otherwise. In those cases, footnotes will specify the percent basis. All summary tables will present a summary of the Exposure treatment group and Standard treatment group. In addition, an overall/total summary will be provided that will include subjects who were replaced.

Individual subject data obtained via the electronic data capture (EDC) system and from external vendors will be presented in listings.

The analyses described in this plan are considered *a priori*, in that they have been defined prior to database lock. Any analysis added after the database lock will be considered *post hoc* and exploratory. *Post hoc* analyses will be labeled as such on the output and identified in the CSR. All analyses and tabulations will be performed using SAS® version 9.3 or higher. Tables and listings will be presented in .rtf or .pdf format. Upon completion, all SAS programs will be validated by an independent programmer. The validation process will be used to confirm that statistically valid methods have been implemented and that all data manipulations and calculations are accurate. Checks will be made to ensure accuracy, consistency with this plan, consistency with tables and consistency between tables and corresponding data listings.

6. Analysis Populations

The Intent to Treat population (ITT) will include all subjects who meet the screening eligibility criteria and are enrolled in the study. A subject will be considered enrolled in the study when they have signed informed consent and received at least 1 treatment of study medication.

The Safety population will include subjects who meet the screening eligibility criteria for the study and receive at least one application of Study drug.

The Exposure population will include those subjects who are assigned to the Exposure cohort and have successfully completed all blood draws (Pre-Application and 2hr, 6hr and 24hr post-application on Day 1). Subjects assigned to the Exposure cohort without successfully completing all blood draws will be replaced and not included in the Exposure population, but will be included in the Intent to Treat and Safety populations.

7. Study Population

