Safety: All subjects who meet the screening eligibility criteria for the study and receive at least one application of Study drug will be evaluated for safety. The following safety parameters will be assessed: 
• Incidence of adverse events (AEs) throughout the study:
○ A subject-by-subject treatment-emergent AE (TEAE) data listing, including verbatim term, preferred term, treatment, severity, and relationship to the Study drug, will be provided.○ The number of subjects experiencing AEs and number of AEs will be summarized by treatment using frequency counts.○ AEs will not include expected local skin reactions such as: minor pain, small blisters, pruritus, erythema, and post-inflammatory pigment changes.○ Reactions to drug administration will be considered an AE if:
▪ Individual blisters develop that are greater than 20mm in diameter. An aggregated blister composed of a number of smaller blisters is not considered an AE.▪ Any medical intervention excluding administration of mild over-the-counter (OTC) pain relievers is required.▪ The event results in discontinuation from the study.

STUDY SYNOPSIS (continued)

Name of sponsor company: Verrica Pharmaceuticals, Inc.
Name of finished product: VP-102 (0.7% w/v cantharidin delivered via a single-use applicator)
Name(s) of active ingredient(s): Cantharidin

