2.2 STUDY POPULATION

There will be up to 40 subjects enrolled with the goal of 16 completing all blood draws in the exposure group. A maximum of 16 will be enrolled in the standard treatment group. The additional 8 subjects may be used for replacement patients. Any subject in the exposure group who does not complete all blood draws may continue to receive treatment, but will be replaced. No more than 16 subjects will be considered as completed Exposure group participants. At least 3 patients in the exposure group will be from 2-5 years of age. Subjects will be considered enrolled when they have signed informed consent and have received at least 1 treatment.

Eligibility will be established by the investigator on the basis of the inclusion and exclusion criteria.

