7.2.2 Sample Size

The primary objective of the study is to determine the presence or absence of systemic cantharidin exposure from application of VP-102. Thus, power calculations were not performed. Data will be summarized using descriptive statistics (sample size, mean, median, standard deviation, minimum, maximum) for continuous variables and frequencies and percentages for discrete variables. Corresponding by-subject data listings will be tabulated. There will be up to 40 subjects enrolled with the goal of 16 completing all blood draws in the exposure group. A maximum of 16 will be enrolled in the standard treatment group. The additional 8 subjects may be used for replacement patients. Any subject in the exposure group who does not complete all blood draws may continue to receive treatment, but will be replaced. No more than 16 subjects will be considered as completed Exposure group participants. At least 3 patients in the exposure group will be from 2-5 years of age. The definition of an enrolled will be those subjects that have signed informed consent and have been treated with at least 1 treatment.

Analysis Populations

Exposure Population: The Exposure population will include all subjects who have valid blood samples measured to assess exposure. This population will be used for the exposure analysis.

Intent-to-Treat Population: The intent-to-treat population (ITT) will include all subjects who meet the screening eligibility criteria and are enrolled in the study. This population will be used for the efficacy analysis.

Safety Populations: The safety population will include subjects who meet the screening eligibility criteria for the study and receive at least one application of Study drug. This population will be used for the safety analysis.

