9.4. Handling of Dropouts or Missing Data

All subjects who receive treatment will be evaluated in the ITT population. Subjects who do not complete all of the scheduled blood draws will be replaced. In the event a subject requests to be removed from the study due to study related adverse events or additional spreading of disease, data will be collected and analyzed as a treatment failure and not replaced.

Unless described otherwise in subsequent sections, analyses will be carried out with the data available using no imputation for missing data. A description of how missing data will be handled for the primary endpoint and secondary endpoints is included below.

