10.5. Subject Reported Spread of Molluscum Lesions

Sibling information will be collected for subjects enrolled in the study. Subjects who have at least one sibling who does not exhibit molluscum lesions at baseline will be considered for this analysis. For those subjects, the count and percent of subjects who had a sibling who was clear at baseline but showed lesions post baseline will be

summarized by treatment group. Note: subjects who do not have a sibling free of molluscum lesions at baseline will not be considered for this analysis.

11. Safety Analysis

All safety analysis will be based on the Safety Population. Analysis using the Safety population will be based on the treatment received.

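### Read literally, the SAP's Safety population can drop a treated subject who fails an eligibility criterion from every safety summary table

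*SAP*

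**What the plan says.** SAP section 6 defines the safety set by two joint conditions: "The Safety population will include subjects who meet the screening eligibility criteria for the study and receive at least one application of Study drug". SAP section 11 then gives that set full scope: "All safety analysis will be based on the Safety Population". The extent-of-exposure, adverse event, local skin reaction (LSR), PERIT and vital sign summaries all follow from it (SAP 11.1 to 11.5).

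The protocol has the same condition, so it does not correct the SAP. Under Analysis Populations in section 7.2.2 it reads: "The safety population will include subjects who meet the screening eligibility criteria for the study and receive at least one application of Study drug". In the synopsis, the Safety paragraph reads: "All subjects who meet the screening eligibility criteria for the study and receive at least one application of Study drug will be evaluated for safety".

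SAP section 6 words the other two populations differently from each other:

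- ITT has the eligibility condition: "The Intent to Treat population (ITT) will include all subjects who meet the screening eligibility criteria and are enrolled in the study". Enrolled means consented and treated at least once, so enrolment does not itself imply eligibility.
- The Exposure population has no such condition: "The Exposure population will include those subjects who are assigned to the Exposure cohort and have successfully completed all blood draws".

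SAP section 9.4, on dropouts and missing data, says: "All subjects who receive treatment will be evaluated in the ITT population".

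**The concern.** A safety set is normally everyone who was exposed to the drug, because a harm counts whether or not the subject should have been dosed. A condition on eligibility removes exactly those subjects whose dosing was a mistake, and their events are ones a reader would want in the rates.

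Safety is a secondary objective here, assessed by incidence tables in at most 40 subjects, so one subject can decide whether an uncommon event appears at all. A treated subject could also be counted in the primary exposure result and be absent from the safety tables of the same report.

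**Working it through.** The documents give no figure to reproduce: there is no power calculation and no assumed rate of ineligible dosing. The check is first textual, then a short illustration of size.

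**Can a treated subject be ineligible?** The investigator establishes eligibility (Protocol 2.2), determines it at screening (4.2.1) and confirms it on Day 1 (4.2.2). An error found later remains possible. Two inclusion criteria in Protocol 2.2.1 also depend on what happens at or after dosing:

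- Criterion 5 concerns bathing and swimming until the drug is removed. It can be checked at screening only if it is read as a promise.
- Criterion 2 puts patients with 21 or more lesions only in the Exposure group, and requires at least 21 to be treated on Day 1. SAP 10.1 and 11.1 foresee lesions left untreated. A subject with, say, 24 lesions of which 18 are treated has been dosed but does not literally meet the criterion. SAP section 3 would place that subject in the Standard group by lesions treated, without saying that the criterion is then met.

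**Does any text restore such a subject to the Safety population?**

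| Text | What it covers | Restores in general? |
|---|---|---|
| SAP 9.4, all treated subjects evaluated | ITT only | No |
| SAP 6, subjects without all blood draws kept in ITT and Safety | Exposure-cohort subjects with incomplete draws | No |
| SAP 5, overall column including replaced subjects | Replaced subjects | No |
| SAP 5, individual data listings | Listings, not rates | No |

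**Is the literal reading consistent with the rest of the SAP?** It is not:

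- ITT in section 6 requires eligibility, while section 9.4 evaluates all treated subjects in ITT. The two agree only if the phrase means passed screening.
- An ineligible Exposure subject with incomplete draws is expressly kept in Safety, while one with complete draws is not. Completing the draws would remove the subject from the safety tables, which cannot be intended.

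**Size per excluded subject.** Let x of n treated subjects have an event, and remove one subject.

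- If the removed subject had the event: (x−1)/(n−1) − x/n = −(n−x)/[n(n−1)].
- If not: x/(n−1) − x/n = x/[n(n−1)].

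The first is largest in size at x = 1 and the second at x = n−1. Both then equal 1/n.

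At n = 40 (the enrolment maximum), n(n−1) = 1,560:

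| Events, all treated | Removed subject had it | Removed subject did not |
|---|---|---|
| 1/40 = 2.5% | 0/39 = 0% (−2.5 points) | 1/39 = 2.6% (+0.1) |
| 10/40 = 25.0% | 9/39 = 23.1% (−1.9) | 10/39 = 25.6% (+0.6) |
| 37/40 = 92.5% | 36/39 = 92.3% (−0.2) | 37/39 = 94.9% (+2.4) |

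The event counts are assumptions. The last row is set near the 92% blistering in the 300-child retrospective study described in Protocol 1.2.2.

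The SAP also tabulates by group, and the Exposure column size is not fixed (16 completers is a goal). At assumed sizes of 24, 16 and 12 the largest shift 1/n is 4.2, 6.25 and 8.3 points.

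**The case against.** The strongest reply is that the phrase means passed screening. It refers to screening criteria, and the protocol leaves the decision to the investigator: "Eligibility will be established by the investigator on the basis of the inclusion and exclusion criteria". Section 9.4 of the SAP, and the sentence in section 6 that keeps subjects with incomplete draws in Safety without any caveat, both fit that reading. A reading that makes a document consistent is normally preferred. Eligibility is rechecked on Day 1, and the synopsis says that subjects who no longer meet criteria are discontinued, so only an error discovered later is left. Any exclusion would also show: SAP 7.1 tabulates the number enrolled and the number in each population, SAP 7.2 tabulates major deviations and lists all of them, and SAP 5 lists individual data. Every figure above assumes an excluded subject, and there may be none.

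Much of this stands. The benign reading is reasonable and may be the intended one, and a silent loss is unlikely. Three things remain:

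- No sentence defines the phrase, so a programmer who flags the Safety set from an eligibility field would be following the SAP as written.
- The supporting sentences reach only ITT, or only Exposure subjects with incomplete draws.
- Disposition counts and listings reveal an exclusion but do not correct an incidence rate. Even the listing is probable rather than certain, because Protocol 7.2.5 describes the adverse event listing for the safety population.

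**Conclusion.** The concern holds. As worded, the SAP allows a treated subject who fails an eligibility criterion to be left out of all safety summaries while counting in the primary exposure table. The size is at most 1/n per excluded subject: 2.5 points overall at 40 subjects, and more within a group column. The most visible consequence is an uncommon event disappearing from the table (1/40 to 0/39).

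This rests on the literal reading and on at least one ineligible subject being dosed. The documents give no rate for that. If there is none, or if passed screening is what was meant and programmed, nothing changes. The exposure result is unaffected and no hypothesis test is involved. The point should be corrected, with medium confidence that it would matter in practice.

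**What to change.** In SAP section 6, define the Safety population as every subject to whom study drug was applied at least once. Define ITT as every enrolled subject, that is, consented and treated at least once. Remove the eligibility condition from both. This also brings the ITT definition into line with SAP 9.4. Ineligible dosing is then reported through the major-deviation table and the by-subject deviation listing already planned in SAP 7.2.

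Protocol 7.2 allows the SAP to modify the planned analysis, and SAP section 9 already does so by analysing treatable instead of treated lesions. No protocol amendment is needed for the analysis, and the protocol wording can be aligned at the next one.

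The cost is two sentences, with no new data and no new outputs. The edit should be made before database lock, because SAP section 5 treats any analysis added after lock as post hoc.
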